
Figure 1. Overview of app functions & categories

[figure not shown]

Procedure

The study is a randomized controlled study. Cluster randomization is used to distinguish three participating schools into control, treatment-as-usual (TAU) and intervention groups. Measures will be obtained at baseline and 42 days later. Participants in both the TAU group and the intervention group receive an approximately 10 minutes long introduction regarding the study specifications and the application. The control group receives no further contact, access to the application or information until study-end questionnaire measures. Participants in the intervention group are randomly assigned to teams consisting of 8 individuals that collectively and individually compete in point collection through completion of in-app health tasks. Participation in the TAU group and intervention group is defined as downloading the Sidekick app and completing at least 3 health exercises within it. Time of exercise is defined as the timestamp on completion of exercise within any of the three types of exercise categories (physical activity, nutrition and mental health) of the app. Exercise frequency refers to how often a given exercise was completed by a participant. Time of attrition was defined as the time stamp of last completing health exercise within the Sidekick throughout intervention period. The procedural difference between TAU group and intervention group evolves around motivational support. The intervention group receives weekly motivational support in form of individual and group feedback on usage, participation in friendly health task competitions and weekly altruistic rewards for usage. Participants in TAU group use the

application individually throughout trial period without any motivational support. A flow chart of participation is displayed in figure 2.

Figure 2. Participant flow chart

Statistical analysis

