Descriptive characteristics of participants along with attrition reason are reported. Pearson's correlation coefficient, independent samples *t*-tests, repeated measures ANOVAs with adjusted alpha levels, and χ^2 tests will be used to measure mean differences from baseline to trial's end within and between research groups on primary and secondary outcome measures. Kaplan-Meier survival analysis plots and logrank tests are deployed to assess time of attrition and possible significant differences between and within research groups [50, 51]. Trial beginning is defined as time of first in-app health exercise completion and the trial period was six weeks, or 42 days, from that moment. Attrition, or the event, is defined as the time of participants' last completed health exercise in SidekickHealth. Participants' cases will be evaluated as censored when the application was still being used 42 days after study start. Cox proportional hazard regression models with interacting covariables using research groups as clusters was used to examine attrition prediction based on usage of in-app health exercises between time, type and frequency of exercises as well as sociodemographic variables (age,

gender) [52]. Significance will be defined at $p < .05$. Data was analysed using IBM SPSS Statistics, Release Version 29 (SPSS, Inc., 2009, Chicago, IL, USA, <http://www.spss.com>).

References

1. Smith, A. (2015, April 1). *U.S. Smartphone Use in 2015*. Pew Research Center. <https://www.pewresearch.org/internet/2015/04/01/us-smartphone-use-in-2015/>
2. Silver, L. (2019, February 5). *Smartphone Ownership Is Growing Rapidly Around the World, but Not Always Equally*. Pew Research Center <https://www.pewresearch.org/global/2019/02/05/smartphone-ownership-is-growing-rapidly-around-the-world-but-not-always-equally/>
3. Anderson, M. & Jiang, J. (2018, May 31). *Teens, Social Media and Technology 2018*. Pew Research Center. <https://www.pewresearch.org/internet/2018/05/31/teens-social-media-technology-2018/>
4. Jones, E. A. K., Mitra, A. K. & Bhuiyan, A. R. (2021). Impact of COVID-19 on Mental Health in Adolescents: A Systematic Review. *The International Journal of Environmental Research and Public*, 18(5). <https://doi.org/10.3390/ijerph18052470>
5. Körmendi, A. (2016). Smartphone usage among adolescents. *Psychiatria Hungarica: A Magyar Pszichiátriai Társaság Tudományos Folyóirata*, 30(3), 297-302.

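### With one school per arm, arm and school effects cannot be separated, yet the plan tests between-arm differences at pupil level at p < .05

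*Combined protocol and SAP*

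**What the plan says.** Allocation is in the Procedure section: "Cluster randomization is used to distinguish three participating schools into control, treatment-as-usual (TAU) and intervention groups". The same section says of the control arm: "The control group receives no further contact, access to the application or information until study-end questionnaire measures". For the two arms with the app: "Participation in the TAU group and intervention group is defined as downloading the Sidekick app and completing at least 3 health exercises within it".

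The Statistical analysis section lists t-tests, repeated measures ANOVAs and χ² tests for baseline-to-end differences "within and between research groups on primary and secondary outcome measures". For attrition: "Kaplan-Meier survival analysis plots and logrank tests are deployed to assess time of attrition and possible significant differences between and within research groups". The threshold is given as "Significance will be defined at" p < .05.

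Two phrases might be read as dealing with clustering. One is "repeated measures ANOVAs with adjusted alpha levels". The other is "Cox proportional hazard regression models with interacting covariables using research groups as clusters was used", in a model meant to predict attrition from the time, type and frequency of exercises and from age and gender.

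The text contains no ICC, design effect, school term or stated limitation on this point.

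**The concern.** Three schools fill three arms, so each arm is one school. Anything that differs between the schools over the six weeks (timetable, staff, peer culture, how the app was introduced) lands in the arm contrast and cannot be taken out. A pupil-level test treats the pupils as independent and counts any such difference as signal.

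The introduction's statement of purpose names the effect of motivational support on attrition as part of the first aim. The control arm has no app, so that question rests on the TAU school against the intervention school. A significant logrank test could be reported as an effect of motivational support when it reflects a difference between two schools. Attrition has no baseline value to adjust for. The app-based primary measures in the Measurements section (the usability score and in-app activity) have no evident pre-app baseline either.

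**Working it through.** **Inputs.** From the documents: 3 schools and 3 arms (Procedure); 661 eligible pupils (Participants); threshold p < .05 (Statistical analysis; sidedness not stated, two-sided assumed); follow-up 42 days. There is no sample size calculation to reproduce. Assumed, because the available text does not give them: ICC, number analysed per school, median time to attrition, and between-school SD of the log hazard. The content of the flow chart (Figure 2) was not available for this check.

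**Step 1: what the design can estimate.** Between-school degrees of freedom = clusters − arms = 3 − 3 = 0. A design matrix with arm and school indicators has rank 3, the same as with arm alone, so no school effect can be estimated beside the arm effect. There are 3! = 6 possible allocations, so a randomization test cannot give p below 1/6 = 0.167. For TAU against intervention there are two mirror-image allocations, so the two-sided p is 1. At the level that was randomized, p < .05 cannot be reached.

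**Step 2: whether either phrase repairs this.**
- The adjusted alpha is attached to the ANOVAs only and is not described as a clustering correction. A stricter threshold would not be one anyway: at an assumed alpha of .0167 with 100 per school, the true error is 5 / 9 / 17 / 34% at ICC 0.005 / 0.01 / 0.02 / 0.05.
- The cluster named for the Cox model is the arm itself, and at most two arms have app data. In a linear-model check with arm as the cluster, the robust standard error of the arm effect collapsed to zero (about 6e-16).

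**Step 3: size for a two-arm mean comparison.** The test uses the within-school variance. With m1 and m2 analysed, the true variance of the difference exceeds the assumed variance by the factor

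inflation = 1 + [2·ICC/(1−ICC)] / (1/m1 + 1/m2)

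and the true error is 2·(1 − Φ(1.96/√inflation)). Example, 50 per school at ICC 0.01: 1 + 0.0202/0.04 = 1.505; 1.96/√1.505 = 1.598; error 11.0%.

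| Analysed per school | ICC 0.005 | 0.01 | 0.02 | 0.05 |
|---|---|---|---|---|
| 50: inflation | 1.251 | 1.505 | 2.020 | 3.632 |
| 50: true error | 8.0% | 11.0% | 16.8% | 30.4% |
| 100: inflation | 1.503 | 2.010 | 3.041 | 6.263 |
| 100: true error | 11.0% | 16.7% | 26.1% | 43.4% |

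At ICC 0 the error is 5%. Simulation (20,000 t-tests per cell) gave 7.9 / 10.8 / 16.8 / 30.1% at 50 and 10.8 / 16.4 / 25.7 / 43.8% at 100.

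**Step 4: size for attrition.** Assume a median of 20 days and a between-school SD s of the log hazard. Event probability by day 42 = 1 − 2^(−42/20) = 0.767; squared standard error of the log hazard ratio = 2/(0.767·m); inflation = 1 + 2s²/SE². For s = 0.1 / 0.2 / 0.3 the true logrank error is 9.6 / 21.8 / 35.3% at m = 50 and 14.0 / 33.1 / 48.6% at m = 100. Simulation (6,000 per cell) gave 10.2 / 22.2 / 33.9% and 14.2 / 32.5 / 47.9%.

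**Step 5: whether more pupils help.** An honest 95% half-width, in within-school SD units, is 1.96·√(1/m1 + 1/m2 + 2·ICC/(1−ICC)). As m grows without limit it stops at 0.196 / 0.279 / 0.396 / 0.636 SD for the four ICCs. For the hazard ratio, the interval cannot be narrower than times-or-divided-by exp(1.96·√(2s²)) = 1.32 / 1.74 / 2.30.

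**The case against.** The strongest reply has four parts.

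- **Baseline measurement.** Change from baseline removes stable differences between schools, and the ICC relevant to change may be smaller. This stands for outcomes measured at baseline, although differences in how schools change over 42 days remain. It does not help attrition, or the app-based primary measures.
- **The Cox model has another job.** It is described as predicting attrition from usage, age and gender, not as the between-arm test. This stands. A reader might infer that the cluster phrase should simply be deleted. The documents do not support that: it is the only place where the group enters the model, and without it two schools would be pooled and their differences could leak into the predictor effects. The phrase could mean robust variance, stratification or interaction; it needs clarifying.
- **The size is assumed.** This also stands. A reader might take all eligible pupils (661/3, about 220 per school) as analysed, which at ICC 0.05 gives an error near 58%. The documents do not support that number: parental consent, the pupil's own agreement and the three-exercise rule all come first. The reward cost in the mHealth application section (50 to 100 dollars at about 50 cents each) implies 50/0.5 = 100 to 100/0.5 = 200 participants, not split by arm.
- **Widening intervals by a guessed ICC does not identify the effect.** This is correct, so such a table is optional. It would also miss correlation within the intervention arm's teams of 8: with 100 per school, ICC 0.005 and an assumed within-team correlation of 0.05 to 0.2, the error after correction is still about 6 to 11%.

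None of these separates arm from school.

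**Conclusion.** The point holds and should be corrected before any between-arm result is reported. The aliasing follows from the counts of schools and arms alone. Its size is illustrative and rests on the assumed ICC, the assumed number analysed and, for attrition, the assumed median and hazard SD. Within the ranges shown, the smallest two-arm mean-comparison error is 8%, and it falls to 5% only if schools do not differ at all.

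A reader might infer two stronger conclusions. One is that the schools do differ, so that a between-arm finding would be false; the documents give no evidence of this, only no means of telling. The other is that the whole study is uninformative. That is not supported: describing attrition over time within an arm, which is the other part of the first aim, is unaffected by the aliasing, and so are predictors of attrition examined within a school.

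**What to change.** 1. In the Statistical analysis section, state that arm and school effects cannot be separated. Report all between-arm results, including attrition, as non-confirmatory estimates with confidence intervals, and do not present p < .05 as evidence of an intervention effect.
2. In the Cox model, replace the use of research groups as clusters with stratification by research group (TAU, intervention). Usage, age and gender effects are then estimated within school, and no between-arm test should be drawn from that model.
3. Optional: add a sensitivity table for two-arm contrasts. For a mean difference, add 2·[ICC/(1−ICC)]·(within-school SD)² to the squared pupil-level standard error over ICC 0.005 to 0.05. For the log hazard ratio, add 2s² to its squared standard error over s = 0.1 to 0.3. The hazard-ratio row needs one extra Cox fit with arm as the only covariate, because the plan lists no arm hazard ratio among its outputs. The table should note that it covers neither correlation within teams nor the three-group ANOVA F-test.

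Cost: analysis wording, one changed phrase and, if the table is added, one extra simple model; no new data. The downside is a weaker between-arm conclusion and, in the table, wider intervals. For a standardised difference over ICC 0.005 to 0.05, the 95% half-width goes from 0.39 to 0.44–0.75 SD at 50 per school, and from 0.28 to 0.34–0.69 SD at 100. Separating school from arm would take several schools per arm, which is a redesign and not part of this fix.

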Physical inactivity and inadequate nutritional habits are often interrelated to disabling emotional problems and integrated strategies should include all three pillars to improve physical as well as mental well-being in adolescent populations. Mobile health interventions targeting disabling emotional problems in adolescent populations have revealed encouraging outcome, despite the fact that attrition rates in these interventions are generally high [11, 25-30]. Varying definitions of attrition have complicated research on this topic but attrition is defined as leaving treatment before obtaining a required level of improvement or completing intervention goals [31-33]. Research on mental mHealth interventions among adolescents have frequently lacked detailed time related attrition data alongside accurate definitions and analysis of attrition reasons though recent studies show promise in that regard [11, 30, 34]. Attrition is regularly reported at two distinct points of time; intervention start and at end of intervention. A continuous measure of usage vs. non-usage in mHealth interventions for adolescents while simultaneously obtaining detailed usage data in order to prevent or delay exact times of attrition in future interventions would perhaps be an improved representation of attrition [35].

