Increased knowledge on actual attrition factors and patterns in adolescent populations from mHealth interventions are direly needed. Obtaining a better understanding of how motivational support motivates adolescents to use mHealth applications and why they maintain or lose interest in using them to improve their health is of vital importance. Motivational support in mHealth interventions, defined as strategies to enhance motivation and counter attrition to overcome behavior change barriers, often include goal-setting, feedback, social support and rewards (36-37). Systematic reviews examining possible drivers behind usage point to group and task customization, localization, functional user support, gamification of health tasks and immediate visual but simplified feedback on user action while while gender-related motivational support features could be contributing factors [36-38]. Timing of tailored motivational support, through just-in-time adaptive interventions (JITAI), should be considered as well when implementing adolescent mHealth interventions since time-based individualization could counter high attritions rates [35, 39]. Given the magnitude of reported health problems among adolescents and lack of cost-effective health behaviour interventions specifically developed for adolescent populations, the need for better understanding of attrition reasons in adolescent mHealth interventions is massive. The purpose of this study was firstly to seek richer understanding of continuous attrition rates from a mHealth intervention in an adolescent population and what effects motivational support has on attrition rates. Secondly, the aim was to examine effectiveness of the intervention with the aim to increase daily mental, nutritional and physical health behaviour.

Methods

Participants

Participants are adolescents, age 13 to 16 years old, attending one of three public schools for children and adolescents in the greater capital area of Iceland. All children attending the oldest 3 classes, called 8th to 10th classes, in three participating public elementary schools in

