SidekickHealth was initially developed through multiple focus group studies amongst both Icelandic elementary school students and adolescents in the obesity clinic at the Landspítali University Hospital in Iceland to incorporate the target groups' needs and opinions. Based on results from focus-group studies and design advisors, the app took the form of a social health game (see Figure 1). Functionality of the app evolves around motivational support to help the user set goals and complete health tasks (gamification of tasks), in three main categories: food and drink (e.g. vegetable and water intake, consumption of fruits, avoiding sugary soda or energy drinks), physical activity (e.g. body-weight exercises, logged minutes of sports activity, gps-based biking, walking or running), and mental health exercises (e.g. reducing stress, exercising gratitude and improving sleep habits). By completing health tasks that are labelled missions and participating in friendly competitions with peers, users earn points (called "kicks") and badges providing altruistic rewards (e.g. litres of water for children in need or polio vaccinations that are sent in their name to children in need through UNICEF). A visual representation of the user's performance is provided in different categories. Keeping the app fun, entertaining, and easy-to-use is of integral importance and was a strong focus point throughout all developmental phases. The smartphone application operates on Android and iOS platforms. The app's function focuses on education and simple health behaviour changes through the benefits of increased physical activity and mental health exercises as well as a healthy diet, portion sizes, and appetite awareness training (AAT). AAT is a behaviour modification tool that has for instance been used in obesity treatment and encourages overweight/obese children and youth to consume food and drink in response to internal appetite cues. It has shown promise for the treatment of overweight and obese children and teenagers and has been visually developed as an individual mission in the app's nutrition category [48, 49]. Participants in the intervention realm will be randomly assigned to groups consisting of 8 individuals which collectively and individually competed in point collection through completion of in-app health tasks. In the beginning of each of the trial's 6 weeks, the intervention group receives in-app messages where a new weekly competition (both individual and on group level) with altruistic rewards is introduced. In weeks 2 to 6, altruistic rewards for past week's efforts will also be handed out. Winners of competitions receive confirmation that UNICEF had sent Polio vaccinations to children in need. Further, through completion of in-app health exercises participants collect litres of water that will be sent in their name to children in need through UNICEF. The total cost for the altruistic rewards for all in-app rewards throughout the treatment period was roughly estimated to be between 50 to 100 US dollars or roughly 50 US cents per participant.

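### Attrition is most likely measured only among app-arm pupils who reach 3 exercises after allocation, so it describes persistence among users and leaves the TAU-intervention comparison open to selection bias

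*Combined protocol and SAP*

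**What the plan says.** The first aim, at the end of the introduction, covers continuous attrition rates and "what effects motivational support has on attrition rates".

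The Procedure section sets the entry rule for the two app arms: "Participation in the TAU group and intervention group is defined as downloading the Sidekick app and completing at least 3 health exercises within it". Control pupils have no app access, so the rule cannot apply to them. The same section refers to a participant flow chart ("A flow chart of participation is displayed in figure 2"), which is not reproduced in the text available for review.

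The Statistical analysis section fixes the clock: "Trial beginning is defined as time of first in-app health exercise completion and the trial period was six weeks, or 42 days". The event is the participant's last completed exercise, and pupils still using the app at 42 days are censored. The arms are compared as follows: "Kaplan-Meier survival analysis plots and logrank tests are deployed to assess time of attrition". Questionnaire and BMI-SDS outcomes are tested "within and between research groups on primary and secondary outcome measures".

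The mHealth application section says that at the start of each of the 6 weeks "the intervention group receives in-app messages where a new weekly competition" is announced. TAU pupils use the same app without motivational support.

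The readable text names no analysis set for the survival analysis or for the questionnaire and BMI-SDS tests. It describes no sensitivity analysis that includes pupils below the threshold.

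**The concern.** The threshold is early app use. It is observed only after the school's arm is set, and it is the kind of behaviour that motivational support is meant to change. The weekly competitions start in week 1 and arrive by in-app message. They could move a pupil who has downloaded the app from 1 or 2 exercises to 3 or more, though by themselves they cannot reach a pupil who has not downloaded it.

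If only pupils past the threshold are counted, two things follow. The reported attrition leaves out the earliest leavers. And the arms are compared after a selection step that may work differently in each, so a difference, or the lack of one, may reflect who was counted rather than how long pupils stayed. If the same rule governs RCADS, GSE, BEARS and BMI-SDS, the two app arms are filtered and control is not, so the contrasts with control are selected too.

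**Working it through.** The plan gives no sample size, power, event count or uptake by arm, so it has no figure of its own to reproduce. Every input below is an assumption unless a source is named. HR is intervention relative to TAU; above 1 means faster attrition under intervention.

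**Step 1. Who is counted when Procedure and Statistical analysis are read together.**

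| Exercises completed | Time zero? | Meets participation rule? | Likely status |
|---|---|---|---|
| 0 | no | no | not counted |
| 1-2 | yes | no | not counted |
| 3 or more | yes | yes | counted |

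No counted pupil can have the event before the third exercise, although the clock starts at the first.

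**Step 2. Level of attrition.** Let q be the share of consented pupils below the threshold and a the day-42 attrition among those counted. Attrition over all consented pupils is a(1-q) + q, so it exceeds a by q(1-a).
- q = 5%, a = 80%: 0.05 × 0.20 = 1 point.
- q = 20%, a = 70%: 0.20 × 0.30 = 6 points (70% reported, 76% over all).
- q = 50%, a = 60%: 0.50 × 0.40 = 20 points.

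This is the gap between two definitions. It is not a bias between arms.

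**Step 3. Comparison of arms.** Suppose half the pupils are committed (all pass, 40% active at day 42) and half are marginal (5% of those who pass are active), with no effect of support after entry. Per 100 consented pupils:

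| Marginal uptake | Counted | Active at day 42 | Active among counted | Active over all |
|---|---|---|---|---|
| 30% | 50 + 15 = 65 | 20 + 0.75 = 20.75 | 31.9% | 20.75% |
| 45% | 50 + 22.5 = 72.5 | 20 + 1.125 = 21.125 | 29.1% | 21.125% |
| 60% | 50 + 30 = 80 | 20 + 1.5 = 21.5 | 26.9% | 21.5% |

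With 30% in TAU and 60% in intervention, the difference is -5.0 points among those counted and +0.75 points over all consented.

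A simulation of this model (6,000 runs, exponential times, two-sided log-rank at 0.05, no school effect) used 50, 100 and 200 consented pupils per arm. The ceiling is about 661/3 = 220 eligible pupils per school on average; 661 is from the Participants section.

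| Marginal uptake, TAU/intervention | HR, 3-exercise set | Rejection at 50/100/200 | HR, all consented |
|---|---|---|---|
| 30/30 | no bias | 5.1/5.0/5.2% | no difference |
| 30/45 | 1.09 | 6.2/7.3/8.8% | 0.95 |
| 30/60 | 1.17 | 8.4/11.5/20.0% | 0.90 |
| 60/30 | 0.86 | 8.7/11.9/19.0% | 1.11 |

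The standard error of the counted difference is 5.4 to 11.1 points, so each shift is below one standard error. Over all consented pupils, rejection at 30/60 is 7.6/9.6/13.8%. That excess reflects the real difference in uptake, which that target includes.

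**Step 4. When does unequal passing bias the comparison?** A second model (220 per arm, 1,500 runs, no arm effect on stopping) lets a shared level of engagement drive both passing and persistence.
- Passing 60%/60%: HR 1.00, rejection 5.3%.
- Passing 60%/80%, related to persistence: HR 1.13, rejection 15.7%.
- Passing 60%/80%, unrelated to persistence: HR 1.00, rejection 5.9%.
- Passing equal at 60%, but a different type of pupil in each arm: HR 0.77, rejection 46%.

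Unequal shares alone are therefore not sufficient for bias, and equal shares do not rule it out.

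**Step 5. Would an earlier time zero help?** Take equal marginal uptake of 45% and assumed mean delays to first use of 10 days in TAU and 3 days in intervention, with 100 to 200 consented per arm. Timing from the introduction date to last exercise, with pupils below the threshold included, gives HR 1.22 to 1.24 and rejection of 21% to 38%. The plan's clock gives about 1.00 and 4% to 6%. Waiting before first use is counted as persistence, which penalises the arm that starts sooner.

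**The case against.** The strongest reply is that no sentence restricts the survival analysis to pupils with 3 exercises. The clock starts at the first exercise, which pupils with 1 or 2 exercises have. The Procedure section also calls pupils participants when they receive the introduction and are put into teams, plausibly before any app use. This stands: a reader might infer that the exclusion is stated outright, but it is only the most likely reading of two sections.

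A reader might also infer that any difference in the share passing biases the comparison. Step 4 shows that it does not unless passing is related to persistence. Such a relation is plausible, since both are app use, but the documents give no data on it.

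A third tempting reading is that the plan contradicts its own definition, because the introduction says "attrition is defined as leaving treatment before obtaining a required level of improvement or completing intervention goals". That sentence summarises the literature, just after noting that definitions vary. The trial's working definition is the last completed exercise, so no contradiction is shown. Persistence among users is a legitimate target; the plan simply does not label it so.

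Finally, all sizes are illustrative, and the flow chart may already give counts by arm. Both points stand, but counts alone would not settle which pupils enter the log-rank test.

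**Conclusion.** The point holds as a gap in definition with a plausible route to selection bias. The participation rule is a usage threshold met after allocation. On the most likely reading it removes non-starters and those who stop after 1 or 2 exercises from a comparison in which support begins in week 1. The result is then persistence among pupils who reached 3 exercises, and it is open to selection bias under either condition shown in Step 4.

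Neither size nor direction can be determined from the documents. The illustrated HRs of 0.86 to 1.17 in Step 3 rest on assumed uptake, retention and numbers consented. They do not support a reading that the trial's comparison is known to be biased, or that it favours a particular arm. No figure is claimed for the contrasts with control, which are affected only if the same rule governs those tests. This should be fixed, mainly because it touches the first aim and the remedy is cheap.

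**What to change.** 1. Do not use the 3-exercise threshold to define the set for the between-arm log-rank test. Keep the clock at first exercise and include every pupil with at least 1 exercise, with those who stop after 1 or 2 as events at their last exercise. Label this persistence among starters, which still conditions on starting.
2. Compare by arm the share of consented pupils with 0, 1-2 and 3 or more exercises. Add a comparison over all consented TAU and intervention pupils, with non-starters as events at time 0 and starters timed from first exercise, labelled as uptake and persistence together. Do not move time zero to the introduction date while the event stays at last exercise.
3. Keep the 3-exercise analysis as a labelled sensitivity analysis.
4. Analyse RCADS, GSE, BEARS and BMI-SDS over all consented pupils in the three schools, regardless of app use.

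The cost is SAP wording and, unless the flow chart already gives it, one table of counts. It needs the list of consented pupils and app logs for those below the threshold; the documents do not say that these are kept, nor whether consent precedes allocation. Reported attrition will look higher. The all-consented estimate mixes uptake with persistence (HR about 0.90 in the 30/60 illustration with no effect after entry). With one school per arm, school and arm remain confounded.
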